6.3 Dosage schedules/modifications

We will use two rounds of experiments, in round 1 we will test all the procedures 1 to 4 of previous section and in round 2 we will test experiments from procedure 5. For each round we will recruit 16 volunteers and in both rounds we will use a cross-over design.

- For round 1 each volunteer will receive 8 procedures; we will use a Latin square design where 16 different sequences of the seven procedures will be created beforehand. The sequences will be allotted to individual volunteers by means of a number draw. This process means that each volunteer will use all of the hand-washing procedures once and will do so in the order prescribed by the randomly selected sequence.
- For round 2, we will use a cross-over design in which the 16 volunteers will be allotted randomly to two groups of the same size. One group will apply the new generated conditions (which will be designed after having results from previous round) and the other will test the control procedure that will be designed to be an appropriate reference condition for the new procedure. In a consecutive run, the two groups will reverse roles (crossover design). At the end of the whole series of runs, every subject will have used each hand-washing procedure once.

7(II). SAFETY REPORTING FOR NON-DRUG TRIALS

7.1 DEFINITIONS

Term	Definition
Adverse Event (AE)	Any untoward medical occurrence in a patient or study participant
Serious Adverse Event (SAE)	A serious event is any untoward medical occurrence that: Results in death Is life-threatening Requires inpatient hospitalisation or prolongation of existing hospitalisation Results in persistent or significant disability/incapacity Consists of a congenital anomaly or birth defect Other 'important medical events' may also be considered serious if they jeopardise the participant or require an intervention to prevent one of the above consequences.

7.2 REPORTING PROCEDURES

Depending on the nature of the event the reporting procedures below should be followed. Any questions concerning adverse event reporting should be directed to the Chief Investigator in the first instance.

The Supertowel has been tested previously and is been considered safe (Appendix 2). There have been no prior adverse events. Therefore, based on this experience no safety issues are anticipated. We don't anticipate that the bar of soap or the sterile oil and soil (used in procedure 4) will produce any adverse effect among participants, as these products are safe and non-pathogenic. For the purpose of this study we use the following definitions for safety reporting:

Definitions used:

Adverse Event (AE): any untoward medical occurrence in a clinical study subject. This includes any incidental findings that may be discovered as a result of the study.

Serious Adverse Event(SAE): any untoward and unexpected medical occurrence or effect that:

- Results in death

- Is life-threatening – *refers to an event in which the subject was at risk of death at the time of the event; it does not refer to an event which hypothetically might have caused death if it were more severe*
- Requires hospitalisation, or prolongation of existing in patients' hospitalisation
- Results in persistent or significant disability or incapacity
- Is a congenital anomaly or birth defect

Medical judgement should be exercised in deciding whether an AE is serious. Important AEs that are not immediately life-threatening or do not result in death or hospitalisation but may jeopardise the subject or may require intervention to prevent one of the other outcomes listed in the definition above, should also be considered serious.

Recording and reporting of procedures:

All adverse events will be recorded and appropriate treatment or referral be provided. For any serious events, the appropriate SAE form should be completed and submitted to the Chief Investigator within 24 hours.

All SAEs will be reported within 24 hours to the Head, Microbiology department from KET's Research Centre/ LSHTM Ethics Committees where in the opinion of the Principal Investigator; the event was thought to be 'related', i.e. resulted from the administration of any of the research procedures.

Contact details for reporting SAEs
Fax:[name] attention to [name]
Please send SAE forms to: [name]
Tel: + (Mon to Fri 09.00 – 17.00)

8. ASSESSMENT AND FOLLOW-UP

The assessment will happen in real-time, then there will be not further follow up of participants. However, participants will be given contact details of the trial manager in case they have further questions.

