3. STUDY DESIGN

To test the efficacy of the Supertowel under the different conditions, we will use a crossover controlled study based and adapted on the protocol of the European Committee for Standardization (EN 1499) which is designed to evaluate the ability of hand-wash agents to eliminate transient pathogens from volunteers’ hands without regard to resident microorganisms. This procedure is based on the “post-contamination treatment” of hands and involves the placement of the test organism (E. coli [ATCC 11229]) on the hands of test subjects, followed by exposure of the test product.

The study will be organized in two rounds of tests. 32 healthy volunteers will be selected for the study. 16 volunteers will be invited for the first round and 16 more for the second round. Each volunteer will receive treatment with all the different procedures the same day of visit to the laboratory.

This is a single centre study conducted in KET’s Scientific Research Centre, Mumbai (India). The recruitment and performance of tests will be done at KET’s Scientific Research Centre, Mumbai (India) Laboratory of India.

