4.4 WITHDRAWAL CRITERIA

Volunteers will be read an information sheet (Appendix 4) where the full study will be explained and where all the procedures for withdrawing from the study will be described. After agreeing to participate in the study, participants will be asked to sign a consent form (Appendix 5).

Participants can withdraw at any time without giving a reason and without having any repercussion. If this is the case, a new volunteer will be recruited and all the data from the withdrawn volunteer will be destroyed.

In the case that a volunteer feels sick or suffers any injury or has a reaction to the product, the participant will be asked to withdraw from the study and appropriate support will be given in the laboratory by [name]. First aid and management of minor health issues will be provided at the laboratory but any more serious health issues will be referred to a nearby health centre. A new volunteer will be recruited and data from withdrawn participant will be destroyed.

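### Section 8 plans no follow-up after the laboratory visit, so adverse events that begin later are recorded only if the volunteer makes contact, although Section 7.2 promises to record them all

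*Combined protocol and SAP*

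**What the plan says.** Section 8 says that assessment takes place in real time and that afterwards "there will be not further follow up of participants". It continues: "However, participants will be given contact details of the trial manager in case they have further questions".

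Section 7.2 makes an unqualified commitment: "All adverse events will be recorded and appropriate treatment or referral be provided". Its definition, "Adverse Event (AE): any untoward medical occurrence in a clinical study subject", has no limit on when the event begins.

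Section 4.4 foresees trouble during testing. "In the case that a volunteer feels sick or suffers any injury or has a reaction to the product", the volunteer is withdrawn, supported in the laboratory or referred, and replaced, and the withdrawn volunteer's data are destroyed. Section 8.1 also has the data of anyone who does not finish all tests destroyed.

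On how long a volunteer is observed, Section 3 says: "Each volunteer will receive treatment with all the different procedures the same day of visit to the laboratory". Sections 6.2.2 and 8.1 also describe a single day. The duration row of the Study Summary instead has each participant attending for 2 days and gives no purpose for the second.

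**The concern.** Section 7.2 promises complete recording, but Section 8 provides no step that would find an event starting after the volunteer has left. Skin irritation need not appear while the hands are still being tested. The protocol itself treats skin condition as relevant: Section 4.2 requires healthy skin without allergy, and Section 4.4 allows for a reaction to the product.

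Two things are at stake. First, a volunteer with a late reaction has, in the protocol body, no stated instruction to report it. Second, Sections 3.2 and 7.2 cite the absence of earlier adverse events, together with the safety data sheet, as grounds for expecting no problem. If this trial also reports none, a reader could take that as further reassurance without knowing that later onset was never actively sought.

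**Working it through.** The plan states no adverse-event rate and no detection target, so there is no figure of its own to reproduce. The check is to set the sections side by side and follow a reaction from onset to record.

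**1. Onset during the visit.** Staff are present. Section 4.4 sets out withdrawal and support, and 7.2 requires a record. This route exists, apart from the data-destruction problem in step 4.

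**2. Onset after the visit.**
- The definition in 7.2 includes the event, because it sets no onset limit.
- The 24-hour limits in 7.2 say how fast a serious event must be reported. They do not define a period over which events are collected.
- Section 8 schedules nothing further, and Section 8.2 closes the trial when the tests are done.
- What remains is the trial manager's contact details. If the volunteer uses them to mention a reaction, 7.2 would require it to be recorded. The details are offered for questions, and no section of the body asks volunteers to report reactions or tells the trial manager to log them.

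Events after the visit are therefore ascertained passively and at the volunteer's initiative.

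**3. What a round 1 volunteer is exposed to.** Section 6.2.2 describes Procedures 1 to 4, each with a treatment and a control: 4 × 2 = 8 conditions. The Supertowel is used in both arms of Procedure 4 and in the treatment arm of the other three: 2 + 3 = 5. Bar soap is the control in the other three: 8 − 5 = 3. If the preparation in 6.2.1 is repeated before each condition, which the text implies but does not state, there are also 8 soap pre-washes and 8 immersions in the contamination fluid. Section 6.3 gives 8 procedures and then refers to seven in the same sentence, so even this count is not settled. Round 2, as described in 6.3, compares a new condition with its control, which is a lighter exposure if only one new condition is tested. The count shows that repeated skin contact in a day is real. It does not show that reactions will occur.

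**4. Whether the record survives.** Sections 4.4 and 8.1 destroy the data of withdrawn and non-completing volunteers. Neither exempts adverse-event records. Read literally, the volunteer most likely to have an event, one withdrawn for a reaction, is the one whose data are destroyed. This conflicts with 7.2 more directly than Section 8 does, and a follow-up call would not cure it.

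**5. Length of observation.** One day (Sections 3, 6.2.2 and 8.1) and 2 days (Study Summary) cannot both describe the same schedule. If a second day follows the exposure day, some later onset could be seen there. Neither version provides anything after the last attendance.

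**The case against.** The strongest case on the other side is that this is a low-risk study. It uses a fabric, bar soap and a non-pathogenic strain in screened healthy men, and Section 10.1 rates the risk as low. Safety is neither an objective (Section 2) nor an outcome (Section 3.1), and no section plans to estimate an event rate. All of that stands. It is a reason to keep the remedy small, but it does not reconcile 7.2 with Section 8.

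Some stronger readings are tempting, and the documents do not support them:

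- **That contact ends and late reactions can never be recorded.** The second sentence of Section 8 provides a contact route, and 7.2 would cover an event reported through it. Late reactions may be missed, but this is not certain.
- **That volunteers are not told to report reactions.** The information sheet (Appendix 4) is not in the text available, so its content cannot be assumed. Only the silence of the protocol body can be stated.
- **That observation lasts a few hours.** No section says so. The text gives one day in some places and 2 days in another.
- **That the gap can be sized by the upper limit for zero events.** With 0 events the one-sided 95% limit is 1 − 0.05^(1/n), which is 8.9% for n = 32 and 17.1% for n = 16. These limits depend on n alone and are the same with or without a follow-up call. They show that a trial of this size says little about rare reactions, but they do not measure what passive reporting loses.

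**Conclusion.** The point holds as a mismatch between a promise and a procedure. Section 7.2 commits to recording all adverse events without a time limit. Section 8 leaves those that begin after the visit to volunteer-initiated contact worded for questions. An adverse-event count from this trial would cover mainly time in the laboratory and could miss later reactions.

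The number missed cannot be estimated, because the documents give neither a reaction rate nor a distribution of onset times. The efficacy comparison is unaffected. The conclusion rests on the protocol body alone. If Appendix 4 tells volunteers to report reactions, the gap is narrower, but ascertainment would still be passive. The point is worth acting on because the remedy is cheap and serves both the volunteers and the interpretation of any safety statement.

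**What to change.** - In Section 8, replace the no-follow-up sentence with one brief scheduled call or text per volunteer a few days after the last visit. Ask one standard question about skin changes or illness and log the answers under 7.2.
- State in Section 8 and in the information sheet that the trial manager's contact details may also be used to report a reaction.
- State the adverse-event collection window in 7.2, and repeat it wherever safety is reported.
- Reconcile Sections 4.4 and 8.1 with 7.2, so that it is clear what happens to adverse-event records when a volunteer's other data are destroyed.
- Reconcile the one-day statements in Sections 3, 6.2.2 and 8.1 with the 2 days in the Study Summary.

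Handling of any event found this way stays as the protocol already provides.

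The cost is 32 short contacts by existing staff, plus one for each replaced volunteer who agrees to be contacted, and a few lines of text. The one downside is that a telephone number must be held until the contact is made. It could be kept with the restricted lookup table described in Section 11.3.

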8.1 LOSS TO FOLLOW-UP

As the experiments will be done with each volunteer at the same day, loss to follow up is not considered in this study. If for whatever reason a volunteer does not complete all the tests, a new volunteer will be recruited and data from the volunteer not completing all tests will not be considered and will be destroyed.

8.2 TRIAL CLOSURE

The trial will close once all the planned tests are done with the 32 volunteers.

9. STATISTICS AND DATA ANALYSIS

For all the procedures, log counts from the left and right hands of each subject will be averaged separately, for both pre and post values. The arithmetic means of all individual \log_{10} reduction values will be calculated. Statistical analysis will be performed with the Statistical Package STATA version 13.0. Wilcoxon matched-pair signed ranks test will be used to test for differences between each *Supertowel procedure* and their reference condition. The new procedure (*Supertowel under different conditions*) will be considered as effective as the reference product (soap) if the mean \log_{10} reduction factor is not significantly smaller for the former than for the latter. Because of the confirmative nature of the test on this application, the level of significance is set at $p = 0.1$. The test is to be used one-sided. The

discrimination efficiency of the test procedure described has been set to detect a difference between the two mean log reduction factors of approximately 0.6 log at a power of 95%. Data and all appropriate documentation will be stored for a minimum of 5 years after the completion of the study.

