3.1 STUDY OUTCOME MEASURES

Reduction of bacteria in pre-contaminated hands of volunteers after using the different test conditions.

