6. TRIAL TREATMENT

6.1 Name and description of investigational treatment product(s)

Supertowel:

The Supertowel is a durable fabric with a permanent anti-microbial treatment. The treated fabric must be dipped in water and then rubbed against the hands so that pathogens will be transferred to the fabric where they will be killed.

Soap:

Non-antimicrobial bar soap will be used as a reference product for three of the experiments.

6.2 Treatment of participants.

6.2.1. Contamination procedure:

The hands of each volunteer will be washed with a non-medicated soap, dried and fingers (up to the proximal interphalangeal joints) will be immersed for 5 seconds in a contamination fluid which contained non-pathogenic *Escherichia coli* (ATCC 11229) 8.3×10^8 cfu/ml. Excess of fluid will be drained off and hands will be air-dried for 3 min.

Pre value. Bacteria will be recovered for the initial pre value by kneading the fingertips of each hand separately for 60 seconds in 10 ml of tryptone soya broth (TSB) without neutralizers. The pre values will be estimated using the Miles *et al.* technique [16].

6.2.2. Hygienic hand-washing procedures/treatments:

Each volunteer will receive the following procedures/treatment in a pre-established random order over the course of one day.

Procedure 1.

- Treatment: Hand cleaning with the Supertowel for 15 seconds.

The Supertowel will be soaked in water by submersing it completely in a bucket filled with tap water. The amount of water absorbed by the ST will be recorded by means of weighing the towel before and after soaking. The volunteers will use the soaked Supertowel for 15 seconds to clean their pre-contaminated hands.

- Control: Hand washing with bar soap and water for 15 seconds.

The control group will wash their pre-contaminated hands with normal bar soap and water for 15 seconds. Hands from volunteers washed with soap will be allowed to dry for 3 minutes.

Prior to doing either of the conditions above, a laboratory technician will demonstrate to the volunteer how to use either the Supertowel or the bar soap for the required time. 15 sec, e.g. wetting hands for 5 seconds, lathering soap for 5 seconds and rinsing hands for 5 seconds).

Procedure 2.

- Treatment: Hand cleaning with a Supertowel that is damp for 60 seconds

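### Section 9 uses the pre count only by subtraction; prespecified covariate adjustment in round 1 would cost little and may improve precision, by an amount the documents do not allow one to fix

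*Combined protocol and SAP*

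**What the plan says.** The outcome in Section 3.1 is "Reduction of bacteria in pre-contaminated hands of volunteers after using the different test conditions", and the study summary expresses it as a log10 reduction. Section 6.2.1 describes the baseline: "Bacteria will be recovered for the initial pre value by kneading the fingertips of each hand separately for 60 seconds". Section 9 then says that "log counts from the left and right hands of each subject will be averaged separately, for both pre and post values", takes the mean of the individual log10 reductions, and adds that "Wilcoxon matched-pair signed ranks test will be used to test for differences between each" Supertowel procedure and its reference. The significance level is 0.1 and "The test is to be used one-sided". The design is said to detect "approximately 0.6 log at a power of 95"%. On numbers, Section 3 says "16 volunteers will be invited for the first round and 16 more for the second round".

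No covariate or regression model appears anywhere. A Supertowel condition counts as equal to soap when its mean log10 reduction is not significantly smaller; no margin is given. The documents state no SD for the pre count, the post count or the paired difference, and no pre-post correlation.

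**The concern.** A log10 reduction is pre minus post. Using it as the analysis variable assumes that a volunteer who starts 1 log higher also finishes 1 log higher. If the true slope differs from 1, the comparison carries variance that a fitted slope would remove. The trial already collects the pre count, so removing that variance needs no new data.

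Each comparison rests on 16 pairs, and the decision rule turns a non-significant result into a claim of equal effectiveness. Under that rule, avoidable noise makes the favourable conclusion easier to reach.

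**Working it through.** **Inputs.** From Sections 3 and 9: 16 pairs per comparison, one-sided alpha 0.1, difference 0.6 log10, power 95%. Assumed, because the documents give nothing: k = SD(pre)/SD(post) and rho = the pre-post correlation, both for the towel-minus-reference paired differences.

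**1. The plan's own figure.** The 95% cannot be reproduced, because no SD is stated. It can only be solved backwards:
- Normal formula: SD = 0.6 × √16 / (1.282 + 1.645) = 2.4 / 2.926 = 0.82.
- Noncentral t on 15 degrees of freedom: SD = 0.797.

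**2. Is there a pre value for each procedure?** Section 9 speaks of pre and post values for all the procedures, and every treatment in Section 6.2.2 starts from contaminated hands. That implies one pre value per procedure. Section 6.2.1 refers to an initial pre value, so the point is not fully explicit. If a single pre value served both halves of a pair, it would cancel in the paired difference and there would be nothing to gain.

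**3. Efficiency against subtraction.** Taking Var(post difference) as 1:
- subtraction: 1 + k² − 2·rho·k
- covariate adjustment (large samples): 1 − rho²

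The ratio (1 − rho²)/(1 + k² − 2·rho·k) never exceeds 1 and equals 1 only when rho = k. For example, at k = 1 and rho = 0.5 it is 0.75/1.00 = 0.75; at k = 0.5 and rho = 0.5 it is 0.75/0.75 = 1.00.

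| k | rho 0 | 0.3 | 0.5 | 0.7 | 0.9 |
|---|---|---|---|---|---|
| 1.0 | 0.50 | 0.65 | 0.75 | 0.85 | 0.95 |
| 0.5 | 0.80 | 0.96 | 1.00 | 0.93 | 0.54 |
| 0.3 | 0.92 | 1.00 | 0.95 | 0.76 | 0.35 |

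Apart from the extreme corner at k = 0.3 and rho = 0.9, the range is about 0.5 to 1.0.

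**4. Effect on power.** The SD is scaled by the square root of the ratio, starting from the SD that gives 95%:

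| Variance ratio | Power at 0.6 log | Difference detectable at 95% power |
|---|---|---|
| 1.00 | 95% | 0.60 |
| 0.90 | 96.4% | 0.57 |
| 0.75 | 98.2% | 0.52 |
| 0.60 | 99.4% | 0.47 |
| 0.50 | 99.8% | 0.42 |

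**5. Price of estimating the slope.** With normal data, the variance of an adjusted contrast is inflated by 1 + 1/(f − 2), where f is the degrees of freedom of the pre values behind the slope.
- One pair of conditions, 16 volunteers: f = 15, so 1 + 1/13 = 1.08. Simulation gave up to 1.09.
- Eight conditions pooled: f = 15 × 7 = 105, so 1 + 1/103 = 1.01. Simulation of the pooled fit with a common slope gave 1.01 to 1.02 at worst, and down to about 0.5 at k = 1 and rho = 0.

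In round 1 the possible loss is therefore 1–2%. In round 2, if it has a single pair of conditions, the loss can reach about 9%.

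**The case against.** The strongest reply is that the size of the gain is unknown. If contamination is well standardised, pre counts may vary less than post counts, which also carry treatment response. At rho = 0.2 the ratio is then 0.91 for k = 0.5 (power 96.2%) and 0.99 for k = 0.3 (power 95.2%), which is negligible. Averaging the two hands already reduces sampling noise. Log10 reduction is the declared outcome in a protocol adapted from EN 1499. The alternative replaces a rank test by a parametric model with a common slope and pooled residual variance across quite different conditions. All of this stands, and it limits how strongly the point can be put.

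A reader might infer several stronger things that the documents do not support:
- **Subtraction adds noise to every comparison.** Subtraction also removes real run-to-run variation in contamination load. Against ignoring the pre count altogether, it loses only when rho is below k/2. At k = 1, the post-only variance is 0.5 times that of subtraction at rho = 0, but 5 times at rho = 0.9.
- **Standardised contamination makes the slope well below 1.** No SD, correlation or assay error is given from which to judge this.
- **Subtraction loses most when the correlation is weak.** That holds at k = 1. At k = 0.5 the ratio is 0.91 at rho = 0.2 and 0.54 at rho = 0.9.
- **The estimate is biased or the endpoint is wrong.** Order is randomised and comparisons are within volunteer, so neither follows.

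The objection does not remove the asymmetry in round 1: a possible loss of 1–2% under a common slope, against a possible gain of up to about half the variance.

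**Conclusion.** The point holds as a refinement of precision. Section 9 fixes the slope at 1 although the data to estimate it are collected. Under assumed SD ratios and correlations, adjustment leaves the variance at about 0.5 to 1.0 times that of subtraction. Power at 0.6 log would then lie between 95% and above 99%, taking the plan's 95% as the starting point. The gain may be nil.

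This rests on a separate pre value before each procedure, a slope common to the conditions, and approximately normal log counts. If slopes differ strongly between conditions, a common slope can lose efficiency, and did so in some simulations.

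The decision rule raises the stakes, but adjustment does not repair that rule. The missing margin and the unstated SD are separate and larger problems.

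**What to change.** In Section 9:
- **State when pre values are taken**: before every procedure or once only. If once only, the rest of this change has no purpose.
- **Round 1, primary analysis**: a linear mixed model of log10 post count with condition, period and log10 pre count as fixed effects and volunteer as random effect, fitted to all round-1 records. Report each Supertowel-minus-reference contrast with its confidence interval. With eight procedures this is 16 × 8 = 128 records; Section 6.3 gives both eight and seven procedures, which must be reconciled.
- **Keep** the mean log10 reduction as the descriptive summary and the Wilcoxon test as a sensitivity analysis.
- **Prespecify the safeguards**: check a condition-by-pre interaction, or use robust standard errors.
- **Round 2**: with possibly one pair of conditions there is little to pool, so the log-reduction analysis may stay primary.

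The cost is SAP wording and a few lines of Stata, with no new data. The downsides to state are the parametric model, the common slope and residual variance, and a loss of 1–2% if subtraction happens to be optimal. If the Wilcoxon test is kept as primary, the minimum is to prespecify the model as a sensitivity analysis.
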